2.3.2 Post-period

During the post-period, the study coordinator and/or other study nurses will identify patients who may be eligible for the study. As in the pre-period, physicians or other appropriate healthcare providers may also identify subjects who are eligible for the study. All hospital staff may be reminded (through posters or memorandums) to inform the study coordinator and/or other study nurses as soon as an ABSSSI subject is seen in the ED. The study coordinator or treating physician will implement the checklist and enroll subjects into the study. Study coordinator will then complete enrollment, including informed consent, and scheduling of follow-up.

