2.1 Overview

This study will employ a “pre-post” pragmatic design, which will consist of both a pre-period, or an observational baseline period, and a post-period, or an interventional period (Figure 1). During the pre-period, each participating site will implement the first component of the critical pathway through implementation of guideline-based criteria to identify patients at the point of care in the ED, obtain informed consent, and monitor enrolled subjects. Sites will initiate treatment for ABSSSI with “usual care,” defined as site- or physician-specific antibiotic treatment of ABSSSI with coverage for a known or suspected Gram-positive infection (e.g., vancomycin, linezolid, and daptomycin) to each study subject who meets all inclusion and exclusion criteria. Blinding of treating physician to subject enrollment in the study during the pre-period will ensure unbiased provision of usual care. During the “post” period, for all subjects who provide informed consent and are subsequently enrolled, each participating site will additionally implement the second component of the new critical pathway, use of dalbavancin, at the point of care in the ED to each study subject who meets all inclusion and exclusion criteria.

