As the study is pragmatic in nature, selection criteria will be minimal and designed to maximize the selection of “real-world” patients who are ideal candidates for treatment in the outpatient healthcare setting, but who are currently admitted to the hospital to receive treatment for ABSSSI. Site training is necessary for both adherence to the protocol and implementation of the new critical pathway, described in greater detail in Section 7, Study sites and administrative structure. Briefly, the core study team in conjunction with members of the contract research organization (CRO) will provide training to other members of the site study team, including all participating site physicians and other healthcare providers (i.e. nurses, pharmacists, and other staff) on protocol adherence and implementation of the new critical pathway. Protocol training will occur before enrolling subjects in both the pre- and the post-period. Before enrolling subjects in the post-period, training on implementation of the new critical pathway will occur over a two- to four-week period after the date of the last enrolled subject in the pre-period. In addition, ongoing reminders and orientations will be scheduled for sites as needed during both the pre- and post-period.

For both periods of interest, subject follow-up will begin on the day of study enrollment and end 44 days subsequently. This will reflect the 10 to 14-day period during which antibiotics are anticipated to be required for care of ABSSSI plus an additional 30 days to ascertain outcomes, such as health resource utilization.

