2.1.2 Rationale of study design

The design of this study allows for a site to understand baseline treatment patterns for ABSSSI, then after this period, to implement an institution-level intervention (i.e., each site contributes study subjects to both treatment arms), as opposed to concurrently across sites (i.e., each site contributes study subjects to a single arm). Use of this design removes site-level variables as a source of potential confounding and enables comparisons of the new critical pathway to usual care in the same setting(s) and similar subject populations.

[figure not shown]
The study is designed in a “pragmatic” fashion (i.e., minimal inclusion/exclusion criteria, which will enable an examination of the impact of the new critical pathway under “real-world” conditions, with good generalizability/applicability to clinical practice.

[figure not shown]
In order to account for temporal trends, sites will also be required to generate data, or reports, on admission rates during the pre- and post-period for other infections, including diabetic foot infections (currently part of exclusion criteria) and pneumonia (a non-skin infection). This will aid in supporting a true difference in outcomes during the pre-period versus the post-period based on the new critical pathway for ABSSSI.

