2.3 Subject identification

Patients presenting to the ED with an ABSSSI infection during both the pre- and post-periods will be assessed for inclusion and exclusion criteria. These criteria will be prepared as an annotated checklist for the study coordinator and/or study nurses to implement and document using a CRF. Information obtained through the annotated checklist coupled with physician assessment will define guideline-based patient identification criteria.

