2.3.1 Pre-period

During the pre-period, the study coordinator and/or other study nurses will identify patients who may be eligible for the study. All hospital staff may be reminded (through posters or memorandums) to inform the study coordinator and/or other study nurses as soon as an ABSSSI patient is seen in the ED. The study coordinator will implement inclusion and exclusion criteria for the new critical pathway by patient interview and/or chart review. Inclusion criteria includes measurement of lesion size through a physician assessment (Appendix A), and clinical judgment that patient requires coverage for a known or suspected Gram-positive infection. Patients who meet all inclusion criteria and none of the exclusion criteria based on study coordinator assessment will be enrolled in the study or flagged for further review by core study team physicians, who will make the final enrollment decision. The treating physician will be blinded to protocol content and study enrollment decision. Study coordinator will then complete all additional elements of enrollment, including informed consent, and scheduling of follow-up.

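### Who applies the eligibility checklist and enrols changes between periods: the treating physician may do both in the post-period, but is blinded to enrolment in the pre-period

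*Protocol*

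**What the plan says.** **Both periods (Protocol 2.3).** On the eligibility criteria: "These criteria will be prepared as an annotated checklist for the study coordinator and/or study nurses to implement and document using a CRF". The next sentence brings physicians in: "Information obtained through the annotated checklist coupled with physician assessment will define guideline-based patient identification criteria".

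**Pre-period (Protocol 2.3.1).** The coordinator applies the criteria by interview or chart review. Patients who pass are enrolled or "flagged for further review by core study team physicians, who will make the final enrollment decision". Lesion size comes from a physician's measurement, and the need for Gram-positive cover is a clinical judgement. On the treating physician: "The treating physician will be blinded to protocol content and study enrollment decision".

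**Post-period (Protocol 2.3.2).** "The study coordinator or treating physician will implement the checklist and enroll subjects into the study". The coordinator then completes consent and schedules follow-up. Neither blinding nor core-team review of flagged cases is mentioned. The subsection also says that physicians and other providers may identify eligible patients just as they could before. Section 2.3.1, however, names only the coordinator and study nurses as identifying patients, with other staff alerting them.

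**Training and rationale.** Training on the pathway before the post-period covers site staff, "including all participating site physicians and other healthcare providers" (Protocol 2.1). Protocol 2.1.2 defends the design on the ground that it "enables comparisons of the new critical pathway to usual care in the same setting(s) and similar subject populations".

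**Analysis.** The primary test is an unadjusted one-sided Pearson chi-square test on admission at the initial episode. A stepwise logistic model with baseline covariates is secondary (SAP 6.2.6.1).

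**The concern.** The two periods enrol different patients without randomisation, so the comparison needs the same selection process on both sides. Here the person who may apply the criteria and enrol changes exactly when the intervention begins. The new selector is unblinded, trained on the pathway, and probably has a say in whether the patient is admitted. That last step is an inference: Protocol 1.2 lists physicians' inexperience with newer agents and their safety concerns among the reasons why patients are still admitted.

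A physician who tends not to enrol patients likely to be admitted would lower the post-period admission rate with no effect of the pathway. One who tends not to enrol patients likely to go home would hide a real effect. Either would act directly on the primary outcome.

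**Working it through.** **1. Passages side by side**

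| Step | Section 2.3 (both periods) | Pre-period, 2.3.1 | Post-period, 2.3.2 |
|---|---|---|---|
| Identifies patients | not assigned | coordinator, study nurses | coordinator, study nurses; also physicians and other providers |
| Runs the checklist | coordinator and/or study nurses | coordinator | coordinator or treating physician |
| Decides flagged cases | not assigned | core-team physicians | not mentioned |
| Treating physician blinded to enrolment | not stated | yes | not stated |
| Physician clinical input | yes | yes (lesion size, clinical judgement) | yes |

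Physician input is common to both periods. What differs is who applies the criteria and who enrols.

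**2. The plan's own power figure**

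Inputs (Protocol 5.3, SAP 6.1.2): 161 per period, one-sided 0.05, 38% versus 23%, power at least 80%.

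Power = Φ[(p1 − p2 − 1.645·SE0)/SE1], with SE0 pooled and SE1 unpooled.

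- SE0 = √(2 × 0.305 × 0.695/161) = 0.0513
- SE1 = √((0.38 × 0.62 + 0.23 × 0.77)/161) = 0.0506
- (0.15 − 0.0844)/0.0506 = 1.296, so power is 90.2%

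With 145 per period (161 less the original 10% attrition assumption in SAP 5.0), power is 87.4%. The plan's statement is reproduced.

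**3. Illustration: admission-bound patients passed over, no true effect**

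Assumed, not in the documents: a share s of admission-bound patients is passed over on the physician route, and a share f = 0.5 of post-period patients comes by that route.

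- Admission rate on that route: q = 0.38(1 − s)/[0.62 + 0.38(1 − s)]
- Post-period rate: r = f·q + (1 − f)·0.38

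For s = 0.2: q = 0.304/0.924 = 0.329 and r = 0.3545. SE0 and SE1 are both about 0.0537, so (0.0255 − 0.0884)/0.0537 = −1.17 and the rejection probability is 12.1%.

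| s | q | r | False-positive rate, n = 161 | n = 145 |
|---|---|---|---|---|
| 10% | 35.6% | 36.8% | 7.8% | 7.6% |
| 20% | 32.9% | 35.5% | 12.1% | 11.6% |
| 30% | 30.0% | 34.0% | 18.4% | 17.4% |

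A simulation of the one-sided Pearson test at n = 161 gave 7.7%, 11.9% and 18.3%. With f = 0.25 the normal-approximation rates are about 6%, 8% and 10%. With f = 1, an upper bound, they are about 12%, 25% and 45%.

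**4. Illustration: discharge-bound patients passed over, planned effect true**

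q = 0.23/[0.23 + 0.77(1 − s)] and r = f·q + (1 − f)·0.23, again with f = 0.5.

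| s | q | r | Power, n = 161 | n = 145 |
|---|---|---|---|---|
| 0 | 23.0% | 23.0% | 90% | 87% |
| 10% | 24.9% | 24.0% | 86% | 83% |
| 20% | 27.2% | 25.1% | 80% | 77% |
| 30% | 29.9% | 26.5% | 72% | 68% |

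With f = 0.25 and n = 161, power is 88%, 86% and 82%, all above the planned 80%.

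**The case against.** **The difference may be deliberate.** Blinding is stated for the pre-period only, to keep usual care unaffected (Protocol 2.1, SAP 3.0), and it cannot continue once physicians deliver the pathway. That stands. A reader might infer a breach of a blinding rule, but no rule extends blinding to the post-period. The point is limited to who selects patients. Unblinded treatment does not require that the treating physician run the checklist.

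**Physicians contribute in both periods, and the coordinator still obtains consent.** Both are true, so the physician does not control enrolment alone. But clinical input is not the enrolment decision, and consent comes after selection. It cannot bring back a patient who was never put forward.

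**The adjusted model addresses imbalance.** It includes SIRS, lesion area, comorbidity, prior treatment failure and insurance, and it may force in covariates that differ between periods. Baseline comparisons and site admission counts help too. These are real but partial safeguards. The model is secondary and can use only measured covariates, and an unrecorded judgement about who will go home is not one of them.

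**The sizes rest on assumptions.** This stands in full. A reader might take the false-positive figures as an estimate of bias in this trial, or as what the fix would remove. They are neither: the skip rates and route share are assumed, and selective referral could produce the same effect after the fix.

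**Timing.** A reader might infer that post-period enrolment could follow the admission decision. The documents do not establish this. Protocol 2.1 places dalbavancin in the ED after enrolment ("for all subjects who provide informed consent and are subsequently enrolled"), the visit schedules are not available to read, and the silence about disposition applies equally to both periods. No timing claim is made here.

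**Conclusion.** The inconsistency is in the text. Section 2.3.2 allows the treating physician to run the checklist and enrol, which differs from 2.3.1 and does not fit the assignment in 2.3. Its statement that physicians could also identify patients in the pre-period does not match 2.3.1 either. In an unrandomised comparison with an unadjusted primary test, this opens an avoidable route to selection bias of unknown direction and size.

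Under the stated assumptions the effect ranges from small (false-positive rate about 6% at a quarter physician route and 10% passed over) to material (about 18% at half and 30%). The documents do not show that selective enrolment occurred or would occur. The change is worth making because it is cheap and uses a process the protocol already has.

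A separate, minor documentation point: Protocol section 5 promises counts of eligible and ineligible subjects for each criterion. SAP 6.2.1 openly replaces this with a listing of ineligible patients and approximate report text on screen failures, but SAP 5.0 does not record the change. This adds nothing to the weight of the main point.

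**What to change.** **Protocol 2.3.2.** Use the route in 2.3.1: the coordinator or a study nurse completes the checklist, core-team physicians decide flagged cases, and the treating physician may refer patients but not enrol them. Reconcile 2.3, 2.3.1 and 2.3.2, including the statement about who could identify patients in the pre-period. This is a short wording change that needs no new staff. Post-period accrual may be slower, and selective referral remains possible.

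**If post-period enrolment has already begun.** SAP version 1.0 is dated 5 February 2019, so the wording change may come too late. If the CRF shows who completed the checklist, add a sensitivity analysis of the primary outcome that compares all pre-period patients with post-period patients whose checklist was completed by the coordinator or a study nurse. State that this subset may differ for other reasons, such as the coordinator's working hours.

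**SAP 5.0.** Add a line, with the reason, saying that the by-criterion screening summary is replaced by the reporting in 6.2.1. Alternatively, restore the summary by period as far as the enrolment logs allow. The logs capture screen failures, but the SAP does not say that they record each criterion.

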2.3.3 Subject follow-up

Within both the pre- and post-periods, follow-up for each subject will begin on the day of enrollment (which is anticipated to be the date of treatment initiation) and conclude 44 days thereafter. Follow-up will therefore include the presumed "episode" of antibiotic therapy for ABSSSI (up to 14 days) and subsequent 30-day period.

2.3.4 Rationale for subject follow-up

Each subject will be followed for a 14-day period (i.e. initial care), which is the longest supported duration of antibiotic therapy for ABSSSI treatment.¹⁵ In order to allow similar opportunity for collection of outcomes in the pre- and the post-period, the post-period similarly assumes 14 days. The addition of 30 days after initial care (i.e. follow-up) was thought to comprehensively assess outcomes during a relevant timeframe after the completion of antibiotic therapy. Therefore, 44 days (initial care and follow-up) for each subject encompasses both the maximum treatment duration and assessment of relevant outcomes in the 30 days following treatment.

2.4 Subject inclusion and exclusion criteria

Study subjects will be recruited among patients who present to EDs of participating sites with ABSSSI and who require coverage for a known or suspected Gram-positive infection. Among all such individuals, attention will be focused on those who meet all of the inclusion criteria and none of the exclusion criteria.

2.4.1 Inclusion criteria

Eligible study subjects satisfy all of the following inclusion criteria^{1,10,11,24}

- Aged ≥ 18 years
- Present to the ED and meet clinical definition for ABSSSI¹⁰⁻¹¹
 - Present with the following infection types: cellulitis/erysipelas, wound infection, or major cutaneous abscess
 - Lesion size area requirements, as measured manually by the length multiplied by perpendicular width of wound (Appendix A).
 - Lesion size area ≥ 75 cm²
- Known or suspected infection caused by susceptible isolates of the following Gram-positive microorganisms: *Staphylococcus aureus* (including methicillin-susceptible and methicillin-resistant strains), *Streptococcus pyogenes*, *Streptococcus agalactiae*, *Streptococcus dysgalactiae*, *Streptococcus anginosus* group (including *S. anginosus*, *S. intermedius*, *S. constellatus*) and *Enterococcus faecalis* (vancomycin susceptible strains).
- Willing and able to return to the hospital or a designated clinic for scheduled visits, or be in contact with the study coordinator through telephone communication, as required by the protocol and the antibiotic treatment administered

2.4.2 Exclusion criteria

Study subjects with any of the following criteria will be excluded^{1,12-14, 26-28,29}

- Known or suspected Gram-negative infections including bacteremia, anaerobic infections, or fungemia, even in the presence of Gram-positive infection
- Known or suspected infections that are severe, life-threatening, or are not included in the ABSSSI FDA guidance, including the following examples:

- [Redacted]
- [Redacted]
- [Redacted]
- [Redacted]
- [Redacted]

■ [Redacted]

- [Redacted]
- [Redacted]
- [Redacted]
- [Redacted]
- [Redacted]
- [Redacted]

[figure not shown]
■ [Redacted]

■ [Redacted]

■ [Redacted]

■ [Redacted]

- Injection drug users presenting with a fever

- 
- Severe neurological disorder leading to severe immobility or confined to wheelchair or bed (e.g. paraplegia and hemiplegia)
 - Bilateral lower extremity involvement of the suspected infection (to exclude patients with chronic venous stasis)
 - Unwilling or unable to follow study procedures

2.5 Early study termination

A premature discontinuation will occur when a subject who signed the informed consent form (ICF) ceases participation in the study, regardless of circumstances, before the completion of all study assessments (i.e., before completing all protocol-stipulated activities). Subjects can be prematurely discontinued from therapy after careful consideration for any one of the following reasons:

- Screen failure
- Failure to receive complete critical pathway by not receiving dalbavancin in the post-period
- Withdrawal of consent (a clear reason will be documented)
- AE (before or after administration of first dose of antibiotic therapy)
- Protocol deviation/violation, including lack of protocol compliance
- Lost to follow-up (every effort will be made to contact the subject)
- Study or site prematurely terminated by the sponsor for any reason
- If a Gram-negative infection including bacteremia, an anaerobic infection, or fungemia develops during the study, or is subsequently found to have been present at baseline, the subject should be removed from study treatment and receive appropriate antibiotic(s) to treat the Gram-negative infection, anaerobic infection, or fungemia.
- Other reasons, such as specified administrative reasons or pregnancy

All subjects who prematurely discontinue from the study, regardless of cause, should have a final assessment at early termination (ET). A final assessment will be

^a If the patient is a woman of child-bearing potential, from at least the first dose of study drug until the final visit she must confirm strict abstinence from sexual intercourse with any male or must confirm use of an effective contraceptive method from the following list: A barrier (condoms, diaphragm or cervical cap) with spermicide; Oral or similar contraceptive, which includes, but is not limited to: injectable, implanted, or patch hormone therapy, and intrauterine device (IUD); Documented surgical sterilization at least 4 weeks prior to baseline; Partner vasectomy at least 6 months prior to baseline.

Within these limits, the specific form of contraception employed are left to the discretion of the patient, and/or the principal investigator, and/or the patient's physician.

defined as either a physical visit or a telephone call that completes the evaluations scheduled for the Final Visit at the end of study (Day 44 visit; refer to Section 4.2, Data collection), or an earlier visit, depending on the visit schedule and when ET occurs. Subjects who do not complete all scheduled visits/procedures will be requested to have an ET Visit. A clear description will be documented and source documentation will be kept by the investigator. The reasons for premature discontinuation from the study will be reflected on the Study Termination page of the CRF.

3 Measures and data collection

3.1 Study outcomes

3.1.1 Baseline characteristics

Baseline characteristics will be collected following subject enrollment into the study, and will be based on physical examination and medical history. A complete list of baseline characteristics is shown in Table 2.

Table 2. Baseline characteristics

Measure Type	Description
Demographics	Age (in years) Gender Ethnicity/Race Employment status Location subject presents from (e.g. from home, LTC, SNF, nursing home)
Comorbidities	Morbid obesity (Body Mass Index) Myocardial infarction Congestive heart failure Peripheral vascular disease Cerebrovascular disease Dementia Chronic pulmonary disease Rheumatologic disease Peptic ulcer disease Mild liver disease Diabetes without complications Diabetes with complications Renal disease Moderate or severe liver disease (Child-Pugh Class B and C)

Measure Type	Description
	
Any malignancy, including leukemia and lymphoma
 
Metastatic solid tumor
 
If subject has cancer, whether active vs. remitted/cured
 
Alcohol/drug abuse/illicit needle use
 
Malnutrition
 
HIV
 
Immunocompromising conditions other than HIV, including:
 
 • Prescribed ≥ 20 mg prednisone per day • Prescribed TNF inhibitors (i.e. infliximab or adalimumab) • Transplant recipient • Active chemotherapy 
Altered mental status
 
Lymphedema or chronic venous stasis
 
Peripheral Vascular Disease

Charlson Comorbidity Index ^b (CCI)	Derived variable based on recorded comorbidities: Calculation of the CCI for each subject at baseline to assess the risk of 1 year mortality
Infection type	Cellulitis/erysipelas, wound infection, or major cutaneous abscess
Infection characteristics	
Lesion size and location
 
Thrombocytopenia (<150,000 platelet count or site-specific definition)
 
Hyperglycemia (>120mg/dL blood glucose or site-specific definition)
 
Hyponatremia (<135 mEq/L blood sodium or site-specific definition)
 
Acidosis (<7.35 pH of the blood or site-specific definition or described in medical chart)
 
Uremia (as described in medical chart)

^b Deyo et al 1992
Allergan Protocol: CMO-US-ID-0476
Version 3.0

Measure Type	Description
	
Anemia (14-18 g/dL hemoglobin for men or 12-16 g/dL hemoglobin for women or site-specific definition)
 
Fever (>98.6 degrees Fahrenheit or site-specific definition)
 
SIRS criteria^c at triage, including highest or lowest recorded RR and highest or lowest recorded BPM in ED/highest or lowest recorded fever in the ED/highest or lowest WBC count in the ED or amount of immature cells in the ED
 
Highest or lowest recorded BP at triage in the ED
 
Laboratory results at baseline and during follow-up (e.g. Total white blood cell count, hemoglobin, sodium, glucose, serum creatinine, and C-reactive protein)
 
Rapid microbial assay and microbiological culture results and type of culture (i.e. blood, wound swab, urine) at baseline and during follow-up
 
Presence of recurrent infection (evidence from chart review, provider assessment and subject report of a similar ABSSSI in the same location on the body) and any ABSSSI infections in the prior 6 months

Healthcare utilization in prior three months	
Hospitalizations and primary reason
 
Surgical interventions and primary reason
 
Admission to the ICU and primary reason
 
ED visits or other outpatient visits (e.g., infusion center and physician's office) and primary reason
 
Use of dialysis
 
Use of any medications for chronic diseases and specifically use of an antibiotic medication
 
Prior antibiotic treatment failure

^c SIRS criteria include abnormalities in temperature, heart rate, respiration, and white blood cell count. Specifically, fever >38.0°C or hypothermia <36.0°C, tachycardia >90 beats/minute, tachypnea >20 breaths/minute or PaCO₂ of less than 32mmHg, abnormal white blood cell count leukocytosis >12,000/microliter, leucopenia <4,000/microliter, or >10% immature cells (bands).^{26,27}

Measure Type	Description
	Receipt of wound care for the presenting infection

